## 6.2. Diet, Fluid, and Activity Control

Subjects are required to refrain from use of tobacco, smoking cessation products, and nicotine-containing products within 3 months prior to Screening through EOT or ET.

Consumption of foods or beverages containing grapefruit/grapefruit juice or Seville oranges or its juice within 7 days prior to Check-in (Day -1) and through EOT or ET will not be allowed.

Consumption of alcohol- or caffeine-containing foods or beverages within 72 hours prior to Check-in (Day -1) and through EOT or ET will not be allowed.

Subjects will refrain from strenuous exercise from 5 days prior to Check-in (Day -1) and during the period of confinement at the CRU and will otherwise maintain their normal level of physical activity through EOT or ET (ie, should not begin a new exercise program or participate in any unusually strenuous physical exertion).

On Day -1 (depending on the time the subject checks into the CRU), subjects will receive breakfast, lunch, dinner, and an optional snack after dinner. On Day 11, subjects will receive breakfast (2 hours after dosing), lunch, dinner, and an optional snack after dinner. On Day 1

and Day 12, subjects will receive a standardized light breakfast (examples of contents are detailed in Table 4) 15 minutes post-repaglinide dose.

Table 4: Example Standardized Light Breakfast Content

Light Breakfast									
Example 1:									
1 hard-boiled egg 1 small piece of toast with butter 1 small apple or banana									
Example 2:									
1 small bowl of cereal or 1 small bagel with cream chees 1 small apple or banana	e								

For the remainder of the time while confined at the CRU, subjects will receive a standard diet at scheduled times that do not conflict with other study-related activities. All study drugs will be administered orally with approximately 240 mL of water. An additional 100 mL of water may be administered if needed.

Fasting requirement in relation to dosing are described in Section 3.1 and Section 5.2.

#### 7. STUDY ASSESSMENTS AND PROCEDURES

#### 7.1. Pharmacokinetic Assessments

## 7.1.1. Pharmacokinetic Blood Sample Collection and Processing

Blood samples for PK analysis of repaglinide and LOXO-305 plasma levels will be collected at the timepoints specified in Appendix 4. The exact time of the study drug administration and the actual time of blood sampling for PK analysis will be recorded on the eCRF.

Processing, storage, and shipping instructions for these PK blood samples will be provided in a separate Laboratory Manual. The number of blood samples and total blood volume required for PK testing is presented in Appendix 3.

# 7.1.2. Analytical Methodology

Plasma concentrations of repaglinide and LOXO-305 will be determined using validated bioanalytical methods. Specifics of the bioanalytical methods will be provided in a separate document.

#### 7.2. Safety and Tolerability Assessments

Safety evaluations may be repeated at the discretion of the Investigator (or designee) or Sponsor.

Every effort will be made to schedule and perform the procedures in accordance with the nominal time, giving considerations to appropriate posture conditions, practical restrictions, and any other procedures to be performed at the same timepoint. The order of priority for scheduling procedures around a timepoint is (in descending order of priority):

- dosing
- PK blood sampling
- vital sign measurements
- 12-lead ECGs
- blood and urine samples for clinical laboratory evaluations
- physical examination.

#### **7.2.1.** Adverse Events

AE definitions; assignment of severity, causality, action taken, and outcome; and procedures for reporting SAEs are detailed in Appendix 1.

Subjects will be asked a non-leading HDYF? Question such as "Have there been any changes in your health status since Screening/since you were last asked?" at the timepoints specified in Appendix 4 (ie, at Screening [after the ICF is signed], at Check-in [Day -1], at each postdose vital sign measurement, and at an appropriate time for all other days). Subjects will also be encouraged to voluntarily report AEs occurring at any other time through the EOS.

Covance Study: 8425120 Protocol Reference: LOXO-BTK-20016

AEs, whether volunteered, identified by the subject's responses to HDYF? Inquiries, or noted on physical examination, ECG, vital sign measurements, or clinical laboratory evaluations, will be recorded throughout the study (ie, from signing of the ICF until EOS [or ET if the subject discontinues from the study and does not complete a follow-up phone call]), either as subject medical history (if the event is reported as beginning prior to signing of the ICF or if the event occurs prior to study drug administration on Day 1 and is assessed as not related to study procedures by the Investigator [or designee]) or as AEs (if the event occurs after signing of the ICF but prior to study drug administration on Day 1 and is assessed as related to study procedures by the Investigator [or designee], or if the event occurs after study drug administration on Day 1 through EOT or ET regardless of relationship to study drug). From EOT or ET through EOS, only AEs assessed as related to study drug by the Investigator (or designee) are to be reported. All SAEs that develop from the time of ICF signing until EOS (or ET, if the subject discontinues from the study and does not complete a follow-up phone call) are to be reported.

Unless a subject withdraws consent or is withdrawn from the study and does not complete the follow-up phone call, all subjects must be followed until EOS. Subjects with AEs that are assessed as related to study drug by the Investigator (or designee) which are ongoing at EOS may continue to be followed until the symptoms or value(s) return to normal, or acceptable levels, as judged by the Investigator (or designee) and confirmed by the Sponsor. The Investigator (or designee) should use appropriate judgment in ordering additional tests as necessary to monitor the resolution of events. The Sponsor may request that additional safety tests be performed.

Subjects will receive a follow-up phone call 7 days ( $\pm$  2 days) after EOT or ET to determine if any SAE or drug-related AE has occurred since the EOT or ET visit.

At all times, a subject may be required to remain at the CRU for longer at the discretion of the Investigator (or designee).

Any event that meets the criteria of a suspected unexpected serious adverse reaction (SUSAR) will be reported to the Institutional Review Board (IRB) according to CRU policy by the Investigator (or designee) and to regulatory authorities by the Sponsor (or Sponsor designee) according to regulatory authority requirements. Refer to Reference Safety Information in the current IB for LOXO-305 for additional safety information.

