#### 1.4.2. Pharmacokinetics

As of March 30, 2020, PK data were available from 107 patients enrolled in LOXO-BTK-18001. Steady-state PK parameters of LOXO-305 in these cancer patients could be derived from data collected on Cycle 1 Day 8 and are shown in Table 1. These data show that LOXO-305 is absorbed after oral administration with a median time to maximum observed plasma concentration (tmax) of approximately 2 hours and has low clearance (Table 1). Due to the limited sampling interval (0 to 8 hours), imputation for the 24-hour sample was made from the Cycle 1, Day 8 predose sample, leading to an estimated plasma half-life of approximately 20 hours. Following administration of doses of 100 mg QD or higher, mean trough plasma levels of LOXO-305 exceeded the IC90 (CCI) ng/mL) of BTK in vitro (Figure 1).

[figure not shown]
Protocol **CONFIDENTIAL** Covance Study: 8425120 Protocol Reference: LOXO-BTK-20016

Table 1: Pharmacokinetic Parameters of LOXO-305 in Cancer Patients (Study LOXO-BTK-18001) at Steady State (Cycle 1 Day 8)

Abbreviations:  $AUC_{0.24}$  area under the concentration-time curve from time 0 to 24 hours; CL/F = apparent oral clearance; Cmax = maximum drug concentration, Geo mean = Geometrical mean, N = number of subjects; PK = pharmacokinetic; QD = once daily; %CV = coefficient of variation in percent;  $t_{1/2}$  = half-life;  $t_{max}$  = time of maximal plasma concentration.

a. N=5; b N=8; c N=18; d N=16; e N=20; f N=16; g N=15 Data cutoff date: March 30, 2020.

Data cutoff date: March 30, 2020

Single doses of 200 mg LOXO-305 were investigated in a study in healthy volunteers (LOXO-BTK-20014, Pilot Food Effect study) in which the PK was determined. Following a single dose of 200 mg LOXO-305 to patients or healthy subjects, area under the concentration-time curve from 0 to 8 hours (AUC0-8) was similar between the two groups and Cmax was approximately 35% higher in healthy subjects, as shown in the table below (data on file at the time of protocol development).

Table 2: Pharmacokinetic of LOXO-305 Following a Single 200-mg Dose of LOXO-305 in Cancer Patients (Study LOXO-BTK-18001, Cycle 1 Day 1) and Healthy Subjects (Study LOXO-BTK-20014)

Parameter	Healthy Volunteers a			Cancer Patients b		
	Geometric Mean	CV	n	Geometric Mean	CV	n
CCI						

Abbreviations: AUC0-8 = area under the concentration-time curve from 0 to 8 hours; CV=coefficient of variation;

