From AE data reported following LOXO-305 administration in 10 healthy volunteers in the LOXO-BTK-20014 study, all TEAEs (headache, nausea, and vomiting) were Grade 1 in severity and considered related to LOXO-305. All 3 events were reported by 1 subject and resolved within 1 to 1.5 days (data on file at the time of protocol development). From preliminary AE data reported following LOXO-305 administration in healthy volunteers in the LOXO-BTK-20006 study, all TEAEs (intermittent belching, bloating, insect bite, aphthous ulcer, nausea, intermittent diarrhea (x2), muscle twitch) were Grade 1 in severity and bloating, intermittent diarrhea and intermittent belching were considered related to LOXO-305. All 7 AEs were reported by 3 subjects and all events resolved prior to EOT; data on file at the time of protocol development). From preliminary AE data reported following LOXO-305 administration in healthy volunteers in Cohort 1 of the LOXO-BTK-20017 study, there was 1 TEAE (headache) observed in the 300 mg LOXO-305 cohort which was Grade 1 in severity and considered related to LOXO-305. The event resolved within 2 hours (data on file at the time of protocol development).

There is a potential risk that multiple doses of LOXO-305 may lead to decreases in white blood cells including neutrophils, lymphocytes, monocytes, and eosinophils. Therefore, to mitigate any potential immunosuppressive risks during the ongoing SARS-CoV-2 (COVID-19) pandemic, subjects will remain in the Clinical Research Unit (CRU) for 100 hours postdose (approximately 5 half-lives) which is Day 16 to allow for LOXO-305 elimination. In addition, subject's hematology laboratory results will be reviewed prior to discharge from the CRU. More information about the known and expected benefits, risks, and reasonably anticipated AEs associated with LOXO-305 may be found in the IB. 

The dosing regimen of the oral dose of repaglinide in the current study is consistent with use in DDI studies. Hypoglycemia is a possible side effect; however, subjects will be given breakfast, lunch, dinner, and an optional snack after dinner on the day before dosing and will have a standardized light breakfast (Table 4)15 minutes postdose to mitigate any potential side effects. The potential risk of participating in this study and receiving this drug is well managed by the study set-up and considered negligible.

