- c. Height collected at Screening only, body mass index based on Screening height.
- d. A complete physical examination will be performed at Check-in (Day -1) and an abbreviated physical examination will be performed at EOT (Day 16) or ET.
- e. The 12-lead ECGs will be obtained at Screening and Check-in (Day -1), Day 1 (predose), Day 2 (predose, 2 hours after LOXO-305 dosing), Day 6 (predose and 2 hours after LOXO-305 dosing), Day 12 (predose, and 2 hours after LOXO-305 and repaglinide dosing), and EOT (Day 16, ie, 96 hours after LOXO-305 and repaglinide dosing on Day 12) or ET. When scheduled at the same time as blood draws, 12-lead ECGs should be carried out prior to and as close as possible to having blood drawn. The 12-lead ECGs will be collected after the subject has rested in the supine position for at least 10 minutes. The allowed sampling window for 12-lead ECGs is ± 30 minutes from the nominal timepoint for all postdose 12-lead ECGs and no less than 10 minutes prior to dosing for predose 12-lead ECGs.
- f. Vital sign measurements (supine blood pressure [BP] and pulse rate) will be obtained at Screening and Check-in (Day -1), Day 1 (predose), Day 2 (predose, 2 hours after LOXO-305 dosing), Day 6 (predose and 2 hours after LOXO-305 dosing), Day 12 (predose, and 2 hours after LOXO-305 and repaglinide dosing), and EOT (Day 16, ie, 96 hours after LOXO-305 and repaglinide dosing on Day 12) or ET. When scheduled at the same time as blood draws, vital sign measurements should be carried out prior to and as close as possible to having blood drawn. BP and pulse rate will be measured using the same arm for each reading after the subject has been supine for at least 5 minutes. The allowed sampling window for vital sign measurements is ±30 minutes from the nominal timepoint for all postdose vital sign measurements and no less than 10 minutes prior to dosing for predose vital sign measurements.
- g. Oral temperature and respiratory rate will be obtained at Screening and Check-in (Day -1), and EOT (Day 16) or ET.
- h. Oxygen saturation will be measured via pulse oximetry once at Screening, Check-in (Day -1), predose on Day 1, and EOT (Day 16) or ET. The allowed sampling window for predose oxygen saturation measurements is no less than 10 minutes prior to dosing.
- i. An HDYF? inquiry will be performed at Screening (after the ICF is signed), at Check-in (Day -1), at each postdose vital sign measurement, and at an appropriate time for all other days.

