- u. The EOT is defined as when the subject is released from the CRU following completion of all assessments through Day 16 (EOT) or ET. The ET is defined as when the subject is released from the CRU if the subject terminates the study early. Vital sign measurements, ECG, and abbreviated physical examination results are to be available for review by the Investigator (or designee) prior to subject release from the CRU at the EOT visit. Clinical laboratory evaluation results for clinical chemistry, hematology, coagulation, and UA and serum pregnancy test results (female subjects only) are to be available for review by the Investigator (or designee) prior to subject release from the CRU at the EOT visit and prior to subject release from the CRU at the ET visit, if available.
- v. Clinical laboratory evaluations and serum pregnancy test (female subjects only) will be performed on the day prior to subject release from the CRU (Day 15) if the subject completes the study (EOT). Clinical laboratory evaluations and serum pregnancy test (female subjects only) will be performed on the day of subject release from the CRU if the subject terminates early (ET).
- w. To be conducted 7 days (± 2 days) following EOT (Day 16) or ET. The EOS is defined as when the subject is contacted by the CRU for a follow-up phone call 7 days (± 2 days) after the EOT visit or ET visit to determine if any SAE or study drug-related AE has occurred since the EOT or ET visit. All subjects who received LOXO-305 (including subjects who are terminated early) will receive a follow-up phone call.

z. Denotes predose sample collection only.

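### Non-serious adverse events judged not related go unreported after early termination, which can come hours after a LOXO-305 dose, so the all-causality tables may under-count early leavers

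*Protocol*

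**What the plan says.** Protocol Section 7.2.1 sets two collection regimes. An event is recorded as an AE "if the event occurs after study drug administration on Day 1 through EOT or ET regardless of relationship to study drug". After that, "From EOT or ET through EOS, only AEs assessed as related to study drug by the Investigator (or designee) are to be reported". The same rule appears in the synopsis, Section 3.1, Appendix 4 footnote j and SAP Section 4. Serious events are collected to end of study (EOS) whatever their cause. If a subject discontinues and does not complete the follow-up call, all collection ends at ET.

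The switch falls at different times after dosing. Appendix 4 places completers' final assessments at "EOT (Day 16, ie, 96 hours after LOXO-305 and repaglinide dosing on Day 12) or ET". For early leavers, footnote u says: "The ET is defined as when the subject is released from the CRU if the subject terminates the study early". It gives no minimum interval after the last dose.

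Section 1.6 gives the reason for watching the days after the last dose: "There is a potential risk that multiple doses of LOXO-305 may lead to decreases in white blood cells". It therefore plans for subjects to stay 100 h postdose, about 5 half-lives.

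Section 7.2.1 says the call 7 (± 2) days after EOT or ET is made "to determine if any SAE or drug-related AE has occurred since the EOT or ET visit". The Appendix 4 grid also marks a How Do You Feel? inquiry and AE/SAE collection at that call.

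SAP Section 8.6.1 tabulates all TEAEs and treatment-related TEAEs separately and gives the TEAE window no end.

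**The concern.** The change from all events to related events is tied to leaving the unit, not to time since the last dose. A completer leaves when most of the drug should have gone; an early leaver may go home with drug still present. From that point a non-serious event is reported only if the investigator calls it related. Appendix 1 defines related narrowly: the timing must fit and no other cause can be identified. Its definition of not related requires that the timing rule causality out. An event with compatible timing and a possible alternative cause fits neither definition, yet that judgement decides whether it is reported.

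The quantity at stake is the all-causality TEAE summary, part of the study's only secondary objective. Early leavers need not resemble completers, since Protocol Section 4.6 lists AEs as a reason for withdrawal. SAP Sections 8.1.1 and 8.1.2 also drop ET measurements from the summary statistics, so the AE tables are one of the few summaries where these subjects' off-drug experience could appear. The SAP's cautious rule, that a missing relationship counts as related, cannot help an event that was never recorded.

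**Working it through.** **Inputs.**
- Half-life: Protocol Section 1.4.2, from patients at steady state with the 24-hour value imputed, "leading to an estimated plasma half-life of approximately 20 hours".
- EOT for completers: 96 h after the Day 12 dose (Appendix 4, footnotes e and f).
- Stated post-dose stay: 100 h (Section 1.6).
- Follow-up call: 5 to 9 days after release, or 120 to 216 h.
- Early release 0 to 24 h after the last dose: an assumption. The documents permit it but give no distribution of ET times.

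**The plan's own figure.** Half-lives covered = hours ÷ half-life. 100 ÷ 20 = 5.0, which reproduces the protocol's approximate 5. First-order residual = 0.5^5.0 = 3.1%.

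**All-causality coverage after the last LOXO-305 dose.**

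| Subject | Hours | Half-lives (÷ 20) | Drug remaining |
|---|---|---|---|
| Completer | 96 | 4.8 | 3.6% |
| ET 24 h after dose | 24 | 1.2 | 43.5% |
| ET 2 h after dose | 2 | 0.1 | 93.3% |
| ET at dosing (limit) | 0 | 0 | 100% |

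Shortfall against completers: 96 − 24 = 72 h to 96 − 0 = 96 h. If the half-life in healthy subjects were 16 to 24 h (an assumption), 96 h would be 6.0 to 4.0 half-lives. The hours do not change.

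**Who the contrast fits.** SAP Section 8.6.1 uses dose-based windows: Day 2 dosing to before Day 12 dosing is LOXO-305 alone, and Day 12 dosing onward is the combination. The 96 h benchmark belongs to the combination column, so the contrast applies directly to someone leaving after the Day 12 dose and before Day 16. A subject leaving on Days 2 to 11 falls in the LOXO-305-alone column. There, completers have only about 24 h (24 ÷ 20 = 1.2 half-lives) after the Day 11 dose before they change column, and the main difference is fewer treated days. The SAP introduces these assignment rules for related TEAEs only; it states no rule for unrelated ones.

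**Can the existing call cover the gap?** After a same-day release the call falls 120 to 216 h after the last dose: 120 ÷ 20 = 6.0 to 216 ÷ 20 = 10.8 half-lives. That is later than both 96 h and 100 h, so one call can look back over the whole window.

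**Possible size (illustration).** The documents give no dropout or event rate. Suppose 1 to 4 of 16 subjects leave early, each with a 5% to 20% chance of a non-serious, unrelated event in a lost 96 h. Expected subjects missed: 1 × 0.05 = 0.05 to 4 × 0.20 = 0.8. As a share of 16, that is 0.3 to 5.0 percentage points.

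**The case against.** The strongest reply is that little is lost. Related events and all serious events run to EOS for anyone who completes the call, so the ET cut-off leaves the treatment-related and serious tables intact for those subjects. The rule is stated consistently, the safety analysis is descriptive, and no comparison of leavers with completers is planned. This stands, and it confines the point to non-serious, unrelated events in the all-causality tables.

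A reader might infer from Section 7.2.1 that the call asks only about serious and drug-related events. The documents do not support that: Appendix 4 schedules the open health question and AE/SAE collection at the call, and subjects are encouraged to volunteer events through EOS. The filter acts on what is reported, not on what is asked.

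A reader might also infer that the white-cell risk would go unseen. Section 1.6 names falls in white cells and possible immunosuppression, and these are followed by laboratory tests. Hematology is reviewed before discharge, laboratory tests are done on the day of release at ET, and the investigator may keep a subject longer. That answer is good but incomplete: footnote u requires ET laboratory results to be reviewed before release only if they are available, and a longer stay is discretionary. Appendix 1 also adds a broader reasonable-possibility sentence on association, which may soften the narrow definition of related in practice.

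**Conclusion.** The point holds in a limited form. Non-serious AEs judged not related that start after ET are not reported, and ET can follow a LOXO-305 dose by hours. Completers are covered regardless of relationship for 96 h, or 4.8 half-lives at 20 h. For release 0 to 24 h after the last dose the shortfall is 72 to 96 h, directly so only for subjects leaving after Day 12 dosing. The all-causality tables may therefore under-count early leavers within the elimination window the protocol itself uses.

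Three stronger readings go too far. That early leavers are certainly under-counted, or the LOXO-305 safety profile certainly understated, cannot be shown without dropout and event rates; the illustration gives under one subject in 16. That the 4.8 half-life contrast applies to every early leaver conflicts with the SAP's treatment windows. That related-only reporting up to EOS is itself a defect for all subjects is a matter of preference, because completers are already past most of the elimination window at EOT.

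This is a cheap improvement to the safety data and does not touch the primary pharmacokinetic analysis. The size rests on the 20 h half-life, the assumed release times and a completed call. If the call is missed, related and serious events are also lost from ET.

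**What to change.** In the protocol synopsis, Section 3.1, Section 7.2.1 and Appendix 4 footnote j, and in SAP Section 4, report all AEs regardless of relationship through EOT or, for ET subjects, through at least 96 to 100 h after the last LOXO-305 dose. Record relatedness, but do not use it as the entry filter within that window. Capture these events at the existing follow-up call, asking for onset dates so that events inside the window can be identified.

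Reword the description of the call in Section 7.2.1 and Appendix 4 footnote w to match the How Do You Feel? and AE/SAE inquiry already scheduled for it. The protocol gives both 96 h (Appendix 4) and 100 h (Section 1.6) for Day 16; reconcile these so that the AE window has one anchor.

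The cost is a wording change and a few more minor unrelated events to record, in at most 16 subjects apart from any replacements. No visit or procedure is added.
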